### 5.2 Handling of Dropouts or Missing Data

For demographics, baseline characteristics, safety profile and other evaluations, each variable will be analyzed using the existing data. Subjects with missing data will be excluded only from the analyses for which data are not available.

There will not be missing data for the primary efficacy endpoint for the mITT and PP based on the definitions of these analysis populations ([Section 4](#)).

For the mITT analysis of the secondary efficacy endpoints, missing VAS scores will be replaced using the multiple imputation (MI) approach. Depending on the pattern of missingness, a two-step process may be employed. If missing data occur for an intermediate visit or time point, they will be imputed first via a Markov Chain Monte Carlo (MCMC) method. As a result, a monotone missingness pattern will be obtained for the data to be fully imputed. The subsequent imputation will use Monotone Regression to produce 5 imputed datasets where the remaining missing data are filled in using 5 different sets of values. The average value of the 5 copies of the VAS scores from MI will be used for each missing data point in the mITT analysis.

To prepare for MI, for subjects who are early discontinued from the study, their VAS scores captured at the termination visit will be assigned to the nearest corresponding scheduled visit. VAS scores to be imputed include those at 15, 30, 45, and 60 minutes post injection and at 2 weeks post injection (prior to touch-up). Other variables that go into the imputation models include treatment, site, and key baseline characteristics such as age, gender, race and Fitzpatrick skin type. When missing VAS score at a given visit or time point is imputed, the values from all its previous visits or time points will be included as predictor in the imputation

model. For example, for a subject with missing VAS at 45 minutes post injection on Day 1, the VAS scores from immediately after injection, 15 minutes and 30 minutes post injection for the subjects will be included in the imputation model.

Other efficacy endpoints will be tabulated using the observed data; no missing values will be replaced in the analyses.

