#### 5.5.1 Primary Efficacy Analysis

The primary efficacy variable is the proportion of responders (to Revanesse Ultra +) immediately after injection, where a responder is defined as a subject who had a within-subject difference (Revanesse Ultra minus Revanesse Ultra +) in VAS pain score of at least 10 mm on a 100-mm scale. The VAS score will be summarized for each treatment and for the within-subject difference with mean, standard deviation (SD), minimum, median, and maximum. The proportion of responders will be summarized with frequency and percentage. A 95% CI for proportion of responders will be constructed using a one-sample binomial exact test. If the lower bound of this 95% CI is greater than 50%, the test product will be claimed to be superior to the comparator product. The primary endpoint will also be summarized by site descriptively.

To assess consistency of treatment effect across study sites, a Pearson's Chi-square test will be performed with respect to the proportion of responders for the mITT population. Due to the low power of the interaction test, a significance level of 0.15 will be used for determining poolability. If the p-value from the Chi-square test is less than 0.15, possible site outlier(s) will be identified and examined. To investigate the impact of these potential site outlier(s), the primary analysis will be performed separately for the site outlier(s) and for the other sites.

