#### 5.5.2 Secondary Efficacy Analysis

The secondary efficacy endpoints are the proportion of responders at 15, 30, 45, and 60 minutes post injection and at 2 weeks post injection (prior to touch-up). Similar method used for the primary efficacy endpoint will be used to analyze the secondary variables.

Missing VAS scores for the mITT analysis will be replaced using the multiple imputation (MI) method. To evaluate the robustness of MI method, subjects with missing VAS scores for the mITT analysis will also be considered in two different ways: (1) as non-responders to the test product (worst case scenario), and (2) as responders to the test product (best case scenario).

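### For the secondary mITT responder endpoints, SAP 5.2 does not name the other fold's VAS at the same time point or the record layout, so the imputation need not preserve the within-subject pairing

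*SAP*

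**What the plan says.** SAP 5.5.1 defines the endpoint as a paired quantity, with the cut in millimetres: "a responder is defined as a subject who had a within-subject difference (Revanesse Ultra minus Revanesse Ultra +) in VAS pain score of at least 10". SAP 5.5.2 carries this over to 15, 30, 45 and 60 minutes and 2 weeks: "Similar method used for the primary efficacy endpoint will be used to analyze the secondary variables".

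Imputation is confined to those secondary endpoints: "For the mITT analysis of the secondary efficacy endpoints, missing VAS scores will be replaced using the multiple imputation (MI) approach". For the primary, "There will not be missing data for the primary efficacy endpoint for the mITT and PP based on the definitions of these analysis populations".

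SAP 5.2 imputes VAS scores, not differences. On covariates it says "Other variables that go into the imputation models include treatment, site, and key baseline characteristics such as age, gender, race and Fitzpatrick skin type". On VAS predictors it says that "the values from all its previous visits or time points will be included as predictor in the imputation" model. Its example is a missing 45-minute score, for which the scores from "immediately after injection, 15 minutes and 30 minutes post injection for the subjects will be included in the imputation model". Five datasets are generated and their average fills each missing score.

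The section does not say whether a record is a subject or a fold, and it names no score from the other fold. The shell of Listing 16.2.6.2.1 shows the Ultra score observed and the Ultra+ score imputed at the same minute, with the difference and responder status derived from that mix.

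**The concern.** Every subject receives both products (Protocol 8.4.2) and rates each fold on the same scale (Protocol 8.6.7). Where one fold is missing, the other fold's score at that minute is an obvious predictor and is half of the endpoint. Where both are missing, the two imputed values should be correlated as observed pairs are.

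A model using only treatment, site, baseline traits and earlier scores carries the between-fold correlation only in part. The imputed difference then has the wrong spread around the 10 mm cut, and subjects fall on the wrong side of it more often than they need to. Two programmers could also build different models from the same text. At stake is the accuracy of the secondary mITT estimates.

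**Working it through.** **The plan's own figures.** The exact binomial test against 50%, upper tail at most 0.025, needs 50 of 80 or 55 of 90 responders. Power is 94.13% (at 70%) and 87.90% (at 68%) with N=80, and 97.26% and 93.31% with N=90. SAP 3.2 prints 94.1, 87.8, 97.2 and 93.3, so the figures reproduce to within 0.1. They concern the primary endpoint, which has no imputed data, so nothing below changes them.

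**Inputs.** From the documents: the 10 mm cut, five imputations averaged, 80 mITT subjects, and the cited predecessor study's responder rates at 15, 30 and 60 minutes (46.7%, 28.3%, 6.7%; SAP Table 1), plus the design rate of 70%. Assumed, because the documents give none: VAS SD σ = 20 mm, time-to-time correlation r = 0.8, between-fold correlation ρ from 0 to 0.9, 10% missing (8 of 80), and correlation ρr between one fold now and the other fold earlier.

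**Closed form, one fold missing, single draws.**
- True SD of the difference: σ√(2(1−ρ)).
- A draw from the fold's own earlier score has covariance r·(ρrσ²) = 0.64ρσ² with the other fold now. The SD of the imputed difference is therefore σ√(2(1−0.64ρ)).
- ρ = 0.5: 20.0 true, 23.3 imputed. ρ = 0.7: 15.5 and 21.0. ρ = 0.9: 8.9 and 18.4.
- At a true rate of 70% the mean lies 0.5244 true SDs above 10 mm. For ρ = 0.7: 0.5244 × 15.49 = 8.12; 8.12/21.01 = 0.387; Φ = 0.65. Imputed subjects respond at 65% instead of 70%, which is −0.5 points overall with 10% missing. For ρ = 0.9: 4.69/18.42 = 0.255; Φ = 0.60; −1.0 points overall.
- Adding the other fold's *earlier* score changes nothing under this structure. Its covariance with the missing score is ρrσ², all of which already runs through the fold's own earlier score (r × ρσ²). Only the same-time score recovers the pairing.

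**Simulation** (3,000 runs per setting; other fold observed). SDs are for imputed draws at a true rate of 70%. Misclassification is among imputed subjects after averaging five copies, shown as fold-level model / model with the other fold.

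| ρ | SD true | SD fold-level | SD with other fold | Misclassified, true 70% | true 46.7% | true 6.7% |
|---|---|---|---|---|---|---|
| 0 | 25.6 | 26.2 | 26.4 | 13.3 / 13.5% | 15.3 / 15.6% | 4.8 / 4.8% |
| 0.3 | 21.3 | 23.6 | 22.3 | 15.9 / 15.5% | 18.6 / 18.4% | 5.4 / 5.3% |
| 0.5 | 18.1 | 21.9 | 19.0 | 18.3 / 17.0% | 20.8 / 19.8% | 6.7 / 5.5% |
| 0.7 | 14.0 | 19.8 | 14.8 | 22.3 / 17.8% | 25.1 / 20.8% | 9.5 / 5.7% |
| 0.9 | 8.1 | 17.5 | 8.6 | 31.2 / 19.1% | 34.6 / 22.9% | 18.5 / 6.5% |

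The simulated true SDs are averages over sets of eight subjects and so sit about 10% below the closed form (18.1 against 20.0). The comparison between columns is what matters. With both folds missing and a true rate of 70%, misclassification is 21.3 / 19.8%, 22.2 / 19.2% and 28.4 / 19.5% at ρ = 0.5, 0.7 and 0.9.

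**Shift in the overall responder proportion**, in points, range over the four true rates, one fold missing:

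| ρ | Fold-level, average of 5 | Fold-level, per dataset | With other fold, average of 5 | With other fold, per dataset |
|---|---|---|---|---|
| 0.5 | −0.1 to 0.1 | −0.3 to 0.3 | −0.3 to 0.2 | 0.0 |
| 0.7 | −0.3 to 0.3 | −0.5 to 0.7 | −0.3 to 0.2 | 0.0 |
| 0.9 | −0.8 to 1.1 | −1.0 to 1.6 | −0.4 to 0.3 | 0.0 |

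With both folds missing, the fold-level average-of-5 shift stays within −0.3 to 0.4 for ρ of 0.5 to 0.9. At ρ = 0 one setting reaches 0.4, where averaging and not layout is the cause. Averaging narrows the imputed differences and partly offsets their excess spread. Correcting only the averaging would therefore enlarge the shift.

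**In subjects.** With 8 imputed, the extra misclassified at a true rate of 70% are 8 × (0.183−0.170) = 0.1 at ρ = 0.5, 8 × (0.223−0.178) = 0.4 at 0.7, and 8 × (0.312−0.191) = 1.0 at 0.9.

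**Testing.** The sequence begins at 15 minutes and needs 50 of 80. At the predecessor's 46.7% the chance of that is 0.3%.

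**The case against.** The strongest reply is that SAP 5.2 is incomplete, not wrong. It never says that folds are separate records and never excludes the other fold. The covariate list is open-ended, and the earlier scores in the example could cover both folds. A reader might infer a fold-level layout because treatment varies only between folds in this design. That does not follow: Listings 16.2.9.1 and 16.2.9.2 carry treatment assignment as one left/right value per subject, so the word could mean side assignment. This stands, and the layout is unspecified. It does not fill the gap, because on either reading the rule names earlier values only and the same-time score on the other fold is still absent.

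It also stands that worst-case and best-case analyses are planned (SAP 5.5.2). Any imputed responder count must lie between them. They bound the answer but do not improve the estimate.

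A reader might also infer that late responder rates would be grossly inflated, by drawing both folds independently. That ignores the SAP's use of earlier scores and its averaging. Take an assumed 60-minute case with mean difference 2 mm, SD 5.33 mm and 6.7% true responders, both folds missing and no predictors. The averaged difference has SD 5.33/√((1−ρ)×5), which is 3.4 mm at ρ = 0.5 and 4.4 mm at 0.7. That gives 0.9% and 3.3% responders, below the true rate.

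**Conclusion.** The point holds as a minor one. For the secondary mITT endpoints, SAP 5.2 does not specify a model that keeps the two folds paired, and the one score most directly tied to the missing one is not named. If the text is followed with earlier scores only, responders among imputed subjects are misclassified somewhat more often: 1 to 5 percentage points more at between-fold correlations of 0.5 to 0.7, and about 12 points at 0.9. The overall proportion moves by about 0.3 points or less up to 0.7 and about 1 point at 0.9. At zero correlation nothing is lost. These sizes rest on the assumed SD, correlations and 10% missing, and scale with the missing fraction.

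It would go too far to say that the responder endpoint as a whole is compromised. The primary has no imputed data, the PP definition requires the scores to be present, and observed pairs stay paired. A changed confirmatory claim is unlikely if the 15-minute rate resembles the predecessor's. The case for acting is that a better model uses data already collected and removes an ambiguity.

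**What to change.** In SAP 5.2, state that:

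- imputation uses one record per subject;
- the model contains both folds' VAS at all time points, including the other fold at the same time point, with site, the listed baseline variables, and side assignment in place of treatment;
- the order of the VAS variables is given, since the monotone step uses only variables placed before the one being imputed. A pattern with one fold missing that breaks this order goes to the MCMC step;
- the difference and responder status are derived within each imputed dataset and the results then combined, replacing classification on the average of five copies.

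The pairing and the per-dataset classification should change together, because either alone leaves a shift. The SAP must then also say how the proportion and its interval are combined, for example by Rubin's rules on the logit scale, since the exact interval in 5.5.1 applies to a single completed dataset.

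Cost: a reshaped input file for the imputation program, a few lines in SAP 5.2, and matching notes to Table 14.2.2.1 and Listing 16.2.6.2.1. No new data are needed, and the primary analysis and sample size are untouched.

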### 5.3 Demographics and Baseline Characteristics

Baseline and demographic characteristic variables (including date of birth, sex, race, ethnicity, and Fitzpatrick skin type) will be tabulated using descriptive statistics. For each continuous variable, the summary will include the mean, standard deviation (SD), median, minimum and maximum. For each categorical variable, the summary will include frequencies and percentages.

Poolability of the data across study sites for key demographic and baseline characteristics (age, sex, Fitzpatrick skin type, Body Mass Index) will be assessed for the ITT population. For age and Body Mass Index, one-way analysis of variance (ANOVA) was performed with study site as the main factor. For Fitzpatrick Skin Type Classification (I-VI), nonparametric Kruskal Wallis test was conducted with study site as the class variable. For sex, Pearson's Chi-square test, or exact test if more appropriate, will be performed.

Demographic and baseline characteristics will be summarized and compared for PP subjects versus non-PP subjects. For categorical variables, comparison will be performed using the Cochran-Mantel-Haenszel (CMH) test for general association adjusted for site. For continuous variables, comparison will be conducted using two-way analysis of variance model (ANOVA) with fixed factors of group and site, with respect to the original values if normality assumption is satisfied, or with respect to ranked values if otherwise.

Descriptive summary of racial distribution within Fitzpatrick Skin Type will be provided for the ITT subjects.

### 5.4 Subject Accountability

A summary of subject disposition will be provided for all subjects descriptively, including reason for discontinuation and analysis populations. Disposition of analysis populations will also be tabulated by study site.

### 5.5 Efficacy Variables

Key efficacy assessments include the following:

- Pain assessment using a visual analog scale (VAS) on a 100-mm scale
- Wrinkle Severity Rating Scale (WSRS): 1=Absent, 2=Mild, 3=Moderate, 4=Severe, 5=Extreme
- Patient Global Aesthetic Improvement (pGAI) Score: 1=Worse, 2=No change, 3=Improved, 4=Much improved, 5=Very much improved
- Investigator Global Aesthetic Improvement (iGAI) Score: 1=Worse, 2=No change, 3=Improved, 4=Much improved, 5=Very much improved

All efficacy analyses will be performed for both the PP and mITT populations. For the primary endpoint, the results from mITT are considered definitive and those from PP supportive.

#### 5.5.1 Primary Efficacy Analysis

The primary efficacy variable is the proportion of responders (to Revanesse Ultra +) immediately after injection, where a responder is defined as a subject who had a within-subject difference (Revanesse Ultra minus Revanesse Ultra +) in VAS pain score of at least 10 mm on a 100-mm scale. The VAS score will be summarized for each treatment and for the within-subject difference with mean, standard deviation (SD), minimum, median, and maximum. The proportion of responders will be summarized with frequency and percentage. A 95% CI for proportion of responders will be constructed using a one-sample binomial exact test. If the lower bound of this 95% CI is greater than 50%, the test product will be claimed to be superior to the comparator product. The primary endpoint will also be summarized by site descriptively.

To assess consistency of treatment effect across study sites, a Pearson's Chi-square test will be performed with respect to the proportion of responders for the mITT population. Due to the low power of the interaction test, a significance level of 0.15 will be used for determining poolability. If the p-value from the Chi-square test is less than 0.15, possible site outlier(s) will be identified and examined. To investigate the impact of these potential site outlier(s), the primary analysis will be performed separately for the site outlier(s) and for the other sites.

#### 5.5.2 Secondary Efficacy Analysis

The secondary efficacy endpoints are the proportion of responders at 15, 30, 45, and 60 minutes post injection and at 2 weeks post injection (prior to touch-up). Similar method used for the primary efficacy endpoint will be used to analyze the secondary variables.

Missing VAS scores for the mITT analysis will be replaced using the multiple imputation (MI) method. To evaluate the robustness of MI method, subjects with missing VAS scores for the mITT analysis will also be considered in two different ways: (1) as non-responders to the test product (worst case scenario), and (2) as responders to the test product (best case scenario).

#### 5.5.3 Other Efficacy Analysis

Other efficacy variables include change in WSRS score from baseline, pGAI, and iGAI at each scheduled post-baseline visit. Descriptive summaries will be provided for each treatment and for within-subject difference.

#### 5.5.4 Interim Analysis

One interim analysis is planned after all subjects have completed Visit 3 or discontinued prior to Visit 3. The purpose is to determine the safety and pain relief of Revanesse Ultra + to support regulatory submissions outside the US that are currently under review for products containing lidocaine. The sponsor does not plan to change the protocol or stop the study based on the results of the interim analysis.

To maintain the integrity of the study, there will be a separate Statistical Analysis Plan for the interim analysis. The interim analysis will be performed by an independent group that is not

involved in the day-to-day trial activities. Access to the interim analysis results will be strictly limited to people who are not directly involved in the study conduct.

Because no change in the study conduct is planned based on the results of the interim analysis, the Haybittle-Peto method will be used to guard the overall Type 1 error rate, with a 0.001 level of significance for the interim analysis and a 0.05 level of significance for the final analysis.

## 5.6 Safety Variables

Key safety variables include incidence rate of treatment-emergent adverse events and the exposure to the study product. They will be summarized using the ITT population.

### 5.6.1 Adverse Events

All adverse events (AEs) occurring during the study will be recorded and coded in the Medical Dictionary for Regulatory Activities (MedDRA), version 15.1 or higher. TEAEs are defined as events that appear subsequent to the first injection or that were present prior to the first injection but worsened in intensity after the first injection. TEAEs may include, but are not limited to, injection site bruising, injection site discoloration, injection site edema, injection site erythema, injection site inflammation, injection site pain, and injection site swelling.

Frequency and percent of subjects reporting TEAEs of injection site reactions will be tabulated for each treatment by system organ class and preferred terms, and further by severity. In summaries of severity, subjects who reported more than one event in a treatment arm that are mapped to the same preferred term will be counted only once in that treatment arm under the strongest severity.

For other AEs where an association with either treatment may not be clearly identified, including systemic TEAEs, frequency and percent of subjects will be tabulated to treated subjects as one group by system organ class and preferred terms, and further by severity and relationship to study device. In summaries of severity and relationship, subjects who reported more than one event that are mapped to the same preferred term will be counted only once under the strongest severity and relationship.

Injection-site TEAEs and non-injection site TEAEs will also be tabulated by subject Fitzpatrick Skin Type (I-IV vs. V-VI) and by number of injections subjects received. Summary by preferred term will further be provided for TEAEs that are reported by subject and for TEAEs that are reported by Investigator separately. Most frequently occurring injection site TEAEs will also be summarized by event's severity and duration.

Treatment-Emergent Serious Adverse Events (TESAEs) will be discussed within the clinical study report. TESAEs and TEAEs that led to treatment interruption or discontinuation will be presented in data listings.

### 5.6.2 Exposure to Study Product

Amount of syringe used will be summarized using descriptive statistics (mean, SD, minimum, median, maximum) at Visit 1 for all the ITT subjects and at Visit 2/Week 2 for those who received a touch-up treatment.

### 5.6.3 Other Variables

Investigator Ease of Use Assessment: overall ease of use of the device will be evaluated by the investigator using the NRS from 0 being not easy to 10 being most easy at Visit 1/Day. It will be summarized for the ITT subjects descriptively with mean, SD, minimum, median, and maximum.

#### Concomitant Medications

Concomitant medications will be coded using the World Health Organization (WHO) Drug Dictionary, Version March 2013, and will be presented in data listings.

## 6 Tables and Listings

The following is an example of tables and listings that will be included in the clinical study report. Tables and listings may be modified as needed during the data analyses.

## 7 Appendices

### 7.1 Handling of Missing or Incomplete Dates for Adverse Events and Concomitant Medications

#### Adverse Events

Handling of partial dates is only considered for the start date. An adverse event with a partial start date is considered treatment emergent if:

- only the day is missing and the start month/year is the same or after the month/year of the first injection
- the day and month are missing and the start year is the same or greater than the year of the first injection date
- the start date is completely missing

